	sensation of vertigo and dizziness as change from baseline
	to month $2\pm 1$ assessed by the Dizziness Handicap
	Inventory (DHI; total).
Secondary Endpoints	• Effect of Vertigoheel ® on QoL as change from baseline to
	month $2\pm 1$ assessed by EQ-5D-5L.
	• Effect of Vertigoheel ® on total sway path as change from
	baseline to month $2\pm 1$ assessed by static posturography.
	• In FD effect of Vertigoheel ® on psychiatric symptoms as
	change from baseline to month $2\pm 1$ assessed by Patient
	Health Ouestionnaire Mood Scale (PHO-9) and
	Generalized Anxiety Disorder Screener (GAD-7)
	• In BVP effect of Vertigoheel ® on vestibular function as
	change from baseline to month 2+1 assessed by video
	head impulse test (vHIT) and/or caloric testing
	• Adverse events (AFs)
	
 
Other observations related to safety (physical examination)
 

	and vital signs)
Study Design	Non-interventional observational prospective monocentric
Study Design	study
Study Population	It is planned to include 20 patients with BVP and 40 patients
	with ED who are going to start Vertigoheel ® treatment
	according to clinical practice at the study conter
	The desision of treatment is up to the physician's discretion
	The decision of treatment is up to the physician's discretion
Inclusion / Evolusion	and is to be made independent of this study.
Criteria	Following documentation criteria should be fulfilled
Cintoina	• BVP (according to the diagnostic criteria of the Bárány
	Society) or FD (according to the diagnostic criteria of the
	Bárány Society).
	• Symptoms for > 3 months of moderate to severe intensity
	according to the DHI [0 (minimum score) -100 (maximum
	score)] of 30 to 90 points.
	• $\geq 18 - 80$ years of age.
	• Legally competent male or female outpatient.
	Signed informed consent.
	• Not pregnant (as proven by negative pregnancy test in
	case of woman of childbearing potential before first
	study drug administration) or breast-feeding.
	Patients with the following conditions are excluded from the
	documentation in this NIS
	• Ongoing (within the last two months) or recently started
	Vertigoheel ® treatment.
	• Debilitating acute or chronic illness (e.g. psychiatric
1	
	illnesses).

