## **1 BACKGROUND AND RATIONALE**

## 1.1 BACKGROUND

Non-interventional studies (NIS) are essential instruments for research institutions, regulatory authorities, and reimbursement bodies in Germany. They are conducted to generate real-life data from clinical practice.

Vertigo is a common symptom with significant adverse effects on patients' QoL. It results from abnormal processing of apparently contradicting information in the central nervous system and is often accompanied by auditory symptoms, making it more difficult for the patient to tolerate. Patients with vertigo suffer from nausea, emesis, sweating, collapse, and tinnitus. Disturbances of equilibrium, systematic imbalance or instability can have negative consequences on the social lives of patients and can be truly disabling.

The leading symptoms of BVP are postural imbalance and unsteadiness of gait that worsens in darkness and on uneven ground. There are typically no symptoms while sitting or lying under static conditions. A minority of patients also have movement-induced oscillopsia while walking. The diagnosis of BVP is based on a bilaterally reduced or absent function of the vestibulo-ocular reflex (VOR). This deficit is diagnosed for the high-frequency range of the angular VOR by a bilaterally pathologic bedside head impulse test (HIT) and for the low-frequency range by a bilaterally reduced or absent caloric response. If the results of the bedside HIT are unclear, angular VOR function should be quantified by a video-oculography system (vHIT). In general, in the long term there is no improvement of vestibular function. There are four treatment options: first, detailed patient counseling to explain the cause, etiology, and consequences, as well as the course of the disease; second, daily vestibular exercises and balance training; third, if possible, treatment of the underlying cause; fourth, if possible, prevention.

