### **3.4 INCLUSION CRITERIA**

Patients will be included in the study if they meet all the following criteria:

- Treatment with Vertigoheel® has been chosen by the physician independently of including the patient in this non-interventional study.
- BVP (according to the current diagnostic criteria of the Bárány Society, 2017) or FD (according to the diagnostic criteria of the Bárány Society, 2017)
- Symptoms for > 3 months of moderate to severe intensity according to the DHI [0 (minimum score) -100 (maximum score)] between 30 to 90 points.
- $\geq 18 80$  years of age.
- Legally competent male or female outpatient.
- Signed informed consent.

• Not pregnant (as proven by negative pregnancy test in case of woman of childbearing potential before first study drug administration) or breast-feeding.

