5.4 Data Analysis

SAS or R software, or an equivalent software package will be used for statistical analysis.

Descriptive statistics will be provided for all parameters. The statistics will be appropriate for the type of data:

- For continuous and count variables, statistics will include the number of observations, mean, standard deviation, median, minimum, maximum, and two-sided 95% confidence interval (CI).

- For categorical variables, the descriptive statistics will include the count and percent of observations in each category along with its Clopper-Pearson two-sided 95% CI. The denominator for the percentage calculation will be based on the number of patients in the analysis population.

This is a non-interventional, observational study, therefore only CI are calculated. All endpoints will be analyzed by the appropriate type of descriptive statistic(s) as described above.

All variables will be analyzed in an exploratory manner. No formal statistical hypothesis testing will be performed.

Missing values will not be imputed.

The following subgroups will be defined:

- Patients with FD
- Patients with BVP

It is planned to include 20 patients with BVP and 40 patients with FD.

No further subgroups will be defined.

Shift tables for physical examination, DHI, Posturography, and vHIT will display the number and percentage of patients per baseline value category vs. the worst value category post-baseline

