14.2.2.2	Quality of Live (EQ-5D-5L)	ITT	Descriptive statistics per question, at Screening Visit and Visit 1, and change from baseline to 2 months
14.2.2.3	Patient Health Questionnaire depression module (PHQ-9)	ITT In patients with FD	Descriptive statistics for total score, at Screening Visit and Visit 1, and change from baseline to 2 months
14.2.2.4	Generalized anxiety disorder scale (GAD-7)	ITT In patients with FD	Descriptive statistics for total score, at Screening Visit and Visit 1, and change from baseline to 2 months
14.2.2.5	Video head impulse test (vHIT)	ITT In patients with BVP	Descriptive statistics at Screening Visit and Visit 1 (not done, normal, pathologic), and change from baseline to 2 months (shift table)
14.2.2.6	Caloric testing	ITT In patients with BVP	Descriptive statistics per parameter, at Screening Visit and Visit 1, and change from baseline to 2 months

14.3	Safety Analyses		
14.3.1	Adverse Events		
14.3.1.1	Overview of adverse events	SP	Number and percentage of patients with adverse events (yes/no), intensity (mild, moderate, severe), causality (related, not related, unknown)

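### For BVP patients who are pathologic on vHIT at baseline, the SAP's vHIT table can register only full normalisation

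*SAP*

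**What the plan says.** The Secondary Endpoints in the protocol's Observational Plan Summary include one that opens "In BVP effect of Vertigoheel". It concerns vestibular function, as change from baseline to month 2, assessed by vHIT and/or caloric testing.

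Protocol section 1.1 gives the diagnostic picture: "The diagnosis of BVP is based on a bilaterally reduced or absent function of the vestibulo-ocular reflex (VOR"). The high-frequency deficit is established "by a bilaterally pathologic bedside head impulse test (HIT"), and the deficit "for the low-frequency range by a bilaterally reduced or absent caloric response". If the bedside test is unclear, "angular VOR function should be quantified by a video-oculography system (vHIT"). Entry under protocol section 3.4 is by published criteria: "BVP (according to the current diagnostic criteria of the Bárány Society, 2017").

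SAP Appendix 1, item 14.2.2.5, specifies the vHIT output in BVP patients as "not done, normal, pathologic), and change from baseline to 2 months (shift table"). SAP section 5.4 names vHIT among the shift-table variables and defines these tables as "patients per baseline value category vs. the worst value category post-baseline". No numeric vHIT variable is named anywhere in the SAP. The next item, 14.2.2.6, handles caloric testing per parameter, with change from baseline.

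**The concern.** The endpoint is a change in function, and the protocol treats vHIT as a way to quantify the reflex. The SAP reduces it to two informative categories, and most BVP patients are expected to sit in the lower one at baseline because of the disease that brought them into the study. A patient who is already pathologic has no worse category to move to, and a real gain that stops short of normal leaves the patient where they were.

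What is at stake is how a table with no shifts is read. It could be taken as stable vestibular function, or as reassurance that nothing deteriorated, when for these patients the scale could show neither. The SAP treats the companion test quantitatively and gives no reason for handling the two components differently.

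**Working it through.** The plan states no figure for this analysis, so there is none to reproduce. The check sets the table specification against the diagnostic text and then illustrates the size of the loss.

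**Inputs**
- vHIT categories: not done, normal, pathologic (SAP Appendix 1, item 14.2.2.5).
- Shift rule: baseline category against worst later category (SAP section 5.4).
- Planned BVP patients: 20 (SAP section 5.4).
- Interval for proportions: Clopper-Pearson, two-sided 95% (SAP section 5.4).
- Loss to follow-up: 10% (SAP section 5.1).
- Not given in the documents: any numeric vHIT value, its SD, or the cut-off for pathologic.

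**Step 1. What each true change looks like in the table**

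| Baseline vHIT | True change | Later category | Table shows |
|---|---|---|---|
| Pathologic | Deterioration | Pathologic | No change |
| Pathologic | Improvement, still below cut-off | Pathologic | No change |
| Pathologic | Improvement past cut-off | Normal | Improvement |
| Normal | Deterioration past cut-off | Pathologic | Worsening |

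The first three rows are where most BVP patients are expected to be. The worst-value rule narrows the third row further: a pathologic result at an unscheduled visit would override a normal Visit 1.

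**Step 2. What a table without shifts would report**

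With 0 of n patients moving to normal, the upper Clopper-Pearson limit is 1 − 0.025^(1/n).
- n = 20: 1 − 0.025^(1/20) = 0.168, so 0% to 16.8%.
- n = 18 (20 less 10%): 1 − 0.025^(1/18) = 0.185, so 0% to 18.5%.
- For comparison, 1 of 20 gives 0.1% to 24.9%.

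These intervals concern the proportion who normalise. They carry no information on the size or direction of change in the reflex.

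**Step 3. Illustration of what is lost**

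Assume that all 20 patients are pathologic at baseline, that numeric results follow a normal distribution truncated at the cut-off, that the untruncated mean lies k SD below the cut-off, and that every patient improves by d = 0.5 SD. The probability of crossing is

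p = [Φ(k) − Φ(k − d)] / Φ(k).

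| k | p | Expected shifts, 20p | Chance of no shift, (1 − p)^20 |
|---|---|---|---|
| 1 | (0.841 − 0.691)/0.841 = 0.178 | 3.6 | 2% |
| 2 | (0.977 − 0.933)/0.977 = 0.045 | 0.9 | 40% |
| 3 | (0.9987 − 0.9938)/0.9987 = 0.005 | 0.1 | 91% |

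The same true improvement can thus give a few shifts or, most likely, none, depending on how far below the cut-off patients start. A mean change would estimate the same 0.5 SD in all three rows. A uniform deterioration would give no shift in any of them. Both k and d are assumptions, so the table shows a range and is not an estimate for this study.

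**The case against.** The strongest reply is that the diagnosis does not fix the baseline vHIT. A reader might infer from protocol section 1.1 that every BVP patient must enter with a pathologic vHIT, so that worsening could never appear. The documents do not support that. The section ties the high-frequency deficit to the bedside test and calls for vHIT when the bedside result is unclear. Entry is by the Bárány Society criteria, which neither document reproduces. A patient with a normal baseline vHIT could move to pathologic and would be counted as worse. This stands: a pathologic baseline is expected for most patients, not required.

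A reader might also infer that the vestibular-function endpoint as a whole is lost. It is not. The endpoint is worded as vHIT and/or caloric testing, and caloric results remain quantitative for the low-frequency range. Vestibular function appears in none of the stated objectives, and the study is descriptive, without hypothesis tests. These points limit the importance of the gap but do not close it for the high-frequency range.

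Nor can it be said that one category per patient hides differences between ears. SAP section 5.4 counts patients, but item 14.2.2.5 does not say whether the category is per side or per patient. That is an ambiguity to settle.

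SAP section 5.4 promises descriptive statistics for all parameters, including mean, SD and interval for continuous ones. If the CRF captures a numeric vHIT value, that rule could arguably cover it. But the SAP names no such variable, the item lists categories only, and the CRF is not among the documents.

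Finally, section 1.1 expects no long-term improvement of vestibular function in general. That tempers hopes for the endpoint. It also makes normalisation, the one change visible for a patient pathologic at baseline, the least likely result.

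**Conclusion.** The point holds for BVP patients who are pathologic on vHIT at baseline, expected to be the majority. For them the specified table can show full normalisation and nothing else. With all 20 pathologic and none normalising, it reports 0/20 with a 95% CI of 0% to 16.8%, whatever the measured reflex did. That interval is illustrative: it assumes a vHIT at both visits in all 20 patients, whereas the plan expects some loss and provides a category for tests not done.

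The loss concerns the high-frequency component of one secondary endpoint in a descriptive study. The conclusion rests on the protocol's own description of BVP and on the absence of any numeric vHIT variable from the SAP. Whether the CRF records one is unknown. This is a worthwhile, low-cost improvement to the SAP; it does not undermine the study.

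**What to change.** In item 14.2.2.5, add the numeric vHIT result for the right and left side at baseline and Visit 1, with change from baseline, mean, SD and 95% CI, in line with the caloric parameters. Name the measure used, since neither document does. Keep the normal/pathologic shift table as supplementary and state whether it is per side or per patient.

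If the CRF already holds the number, the cost is SAP wording and one table. If it holds only the category, the values must be transcribed from source: at most 20 patients × 2 visits × 2 sides = 80 numbers, plus a small eCRF addition with its data checks, queries and investigator approval. Protocol section 9 names vHIT among the outcome sources and requires original source documentation to be kept, so no extra test on patients should be needed.

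If the numeric result cannot be retrieved, the SAP and the report should say that, for patients pathologic at baseline, the table can show only normalisation, and that the absence of a shift is not evidence of stable vestibular function.
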